Are Sugar-Sweetened Beverage Information Labels Well-Targeted?

NCT05038163

Statistical Analysis Plan

April 1, 2021

Are Sugar-Sweetened Beverage Information Labels Well-Targeted? Evidence and Welfare Implications

Sample Size and Power

The goal of this experiment is not to accept or reject a particular hypothesis, but rather to measure the targeting properties and welfare effects of information labels with statistical precision. Thus, our power calculations are based on 95%-confidence intervals.

We use related preliminary work to estimate our standard errors for this project; a summary of this early work is available at the end of this document. In our preliminary work, each label was assessed with approximately 180 participants, with 90 assigned to a control arm and to each of two labels, and the 95%-confidence intervals for the treatment effects have width of about \$0.50 per item, or roughly 25% of the average estimated bias. For our proposed project, a sample size of approximately 3,000 subjects will give us a total sample of 1,000 to assess each label (i.e., 500 from the control and 500 from the treatment group). Assuming the same variances as in our preliminary work, this will give us standard errors that are $\sqrt{1000/180} \approx 2.4$ times smaller than in our preliminary work. Our 95%-confidence intervals for our treatment effects will have width of approximately \$0.21 per item, or roughly 10% of the average estimated bias. Under the same assumptions, our 95%-confidence intervals for our targeting measure (i.e., the covariance) will be approximately 2.4 times smaller than in our preliminary work and have width of approximately 0.26 dollars squared.

For the subsample of older adults, we will have approximately 250 participants to assess each label (i.e., 125 from the control and 125 from the treatment group). If we assume the variances on the treatment effects and measure of targeting are the same as for the full sample, then we can again predict power. Under this assumption, we will have standard errors that are $\sqrt{250/180} \approx 1.4$ times smaller than in our preliminary work. Our 95%-confidence intervals for our treatment effects will have width of approximately \$0.36 per item, or roughly 20% of the average estimated bias for the full population. Similarly, our 95%-confidence intervals for our targeting measure (i.e., the covariance) will have width of approximately 0.45 dollars squared.

Statistical Design

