2. When the government can additionally set an optimal tax or subsidy, the incremental welfare from the information label is:

$$\left(\frac{1}{2} \text{Var}[\tau] + \text{Cov}[\tau, \gamma] \right) D_p(p)$$

The proposition states that the welfare effects of the information label depend on two terms: the heterogeneity of treatment effects, $\text{Var}[\tau]$, and the extent to which the treatment effects are well-targeted, $\text{Cov}[\tau, \gamma]$. Welfare is decreasing in $\text{Var}[\tau]$ holding constant $\text{Cov}[\tau, \gamma]$, as this large un-targeted heterogeneity generates misallocation in which individuals purchase which products. the extent to which it reduces the variances of bias: $\text{Var}[\tau + \gamma] - \text{Var}[\gamma]$. To obtain some intuition for this result, note that $\frac{1}{2} \text{Var}[\tau] + \text{Cov}[\tau, \gamma] = \text{Var}[\tau + \gamma] - \text{Var}[\gamma]$. Since $\tau + \gamma$ represents the “post-label” bias, the welfare effects of the label are thus proportional to how much the label reduces (or increases) the variance of bias in the population.

In the absence of a financial instrument, the welfare effects of the label also depend on $E[\tau]^2 + 2E[\tau]E[\gamma]$. Note that these terms are functions of $E[\tau]$, the average treatment effect. Intuitively, even if the label does not reduce the variance of bias, and instead simply functions as a blunt policy instrument that affects everyone in the same way, it is still useful because it functions as a substitute for a tax. The term $\rho \mu E[\tau|p] D_p$ simply corresponds to the extent to which labels counteract (or amplify) market power. E.g., if firms price too high, then a modest bias that leads consumers to overestimate the marginal value of the product may be optimal.

Econometric details. Recall that in the experiment, all subjects first make a decision in the absence of any labels (decision set $j = 1$), and then again with the potential presence of a label (decision set $j = 2$). We decompose willingness to pay of person i in decision set $j \in \{1,2\}$ for product k in label treatment T as follows:

$$w_{ijk}(T) = v_{ijk} + \gamma_{ik} + \tau_{ik}(T) \cdot I(j = 2)$$

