where $\tau_{ik}(T)$ is the treatment effect on person i for product k , γ_{ik} is the bias, and v_{ijk} is the true cost or benefit of getting the sugary rather than the sugarless drink. Our multiple price lists provide direct estimates of $w_{ijk}(T)$. We obtain estimates of bias, $\widehat{\gamma}_{ik}$, using the methodology of [name], Lockwood, and [name] (2019a) and the stage 1 survey questions. Before we detail the methodology of obtaining these estimates, we summarize the approach we take with those estimates in hand.

We make the following identifying assumptions, which essentially state that the measurement error in $\widehat{\gamma}$ is independent of the treatment effects.

$$E[v_{ijk}|T] \text{ does not depend on } T \text{ or on } j$$

$$\text{Cov}[v_{i2k} - v_{i1k}, \tau_{ik}] = 0$$

$$\text{Cov}[\gamma_{ijk} - \widehat{\gamma}_{ijk}, \tau_{ik}] = 0$$

$$\text{Cov}[\gamma_{ip} - \widehat{\gamma}_{ik}, v_{ijk} - v_{ij'k}] = 0$$

Under these assumptions, we obtain the following equation for the average (across the six products) variance of a given label:

$$\frac{1}{6} \sum_j Var[\tau_j | T = t] = \frac{1}{6} \sum_j (Var[\Delta w_{ij} | T = t] - Var[\Delta w_{ij} | T = 0])$$

Where $\Delta w_{ij} := w_{ij2} - w_{ij1}$ is the difference in WTP for the same product-pair $\$j\$$ before seeing the label versus after seeing the label.

We also obtain the following formula for the average covariance of the label with the bias:

$$\frac{1}{6} \sum_j Cov[\tau_j, \gamma_j | T = t] = \frac{1}{6} \sum_j (Cov[\Delta w_{ij}, \hat{\gamma}_i | T = t])$$

From this, it we can also immediately obtain the following statistics:

$$Var[\tau + \gamma] - Var[\gamma] = Var[\tau] + 2Cov[\tau, \gamma]$$

$$E[(\tau + \gamma)^2] - E[\gamma^2] = Var[\tau] + 2Cov[\tau, \gamma] + E[\tau]^2 + 2E[\tau]E[\gamma]$$

Estimating bias. We estimate each participant's bias using methods from [name], Lockwood, and [name] (2019a). Specifically, we assume bias is driven by a lack of nutritional knowledge and/or a lack of self-control.

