To estimate each individual's nutritional knowledge, we compute a nutrition score, $nutrition_i$. This score ranges from 0 to 1, where higher values indicate more nutritional knowledge. To get this score, in the first stage of the experiment we ask participants 24 questions about their nutritional knowledge. Some of these questions include multiple parts, leading to a total of 59 sub-questions. As in [name], Lockwood, and [name] (2019a), we compute their nutritional knowledge score by calculating how many of the 59 sub-questions they answered correctly, and converting this into a percentage. In our preliminary work, the average score is 68%, the 10th percentile is 44%, the 25th is 61%, the 50th is 69%, the 75th is 78%, and the 90th is 85%.

To estimate each individual's self-control $selfcontrol_i$, we ask participants to answer the following question: "Please indicate how much the following statement reflects how you typically are: I drink soda pop or other sugar-sweetened beverages more often than I should." We then convert this response to a 0 to 1 scale (0 = Definitely, 1/3 = Mostly, 2/3 = Somewhat, 1 = Not at all).

We convert the proxy variables into a proxy for bias via equation (26) from [name], Lockwood, and [name] (2019a):

$$\hat{\gamma}_i = [\hat{\tau}_1 \cdot (0.92 - nutrition_i) + \hat{\tau}_2 \cdot (1 - selfcontrol_i)] \cdot p_i / \hat{\zeta}_i^c$$

Here 0.92 is the average score among nutrition experts to the nutrition knowledge quiz (per [name], Lockwood and [name], 2019a) and 1 represents perfect self-control.

While we eventually plan to estimate using the Homescan data, for now we use the point estimates from [name], Lockwood and [name] (2019a). Specifically, we use $\hat{\tau}_1 = 0.854$ and $\hat{\tau}_2 = 0.825$, as reported in Table 5, column 1 of their paper. We also set $p = 3.63$ and $\hat{\zeta}_i^c = 1.39$, the averages reported in Table 6 of their paper. Finally, we rescale so that bias is in terms of $\$$ per 144 ounces (i.e., $\$$ per 12-pack, since all drinks in our sample come in 12 oz containers).

In our sample, $E[\hat{\gamma}_i] = 1.95$, with a standard deviation of 1.26.

[figure not shown]
Related Preliminary Work

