To ensure that our statistical methods are sufficiently well-powered, we have already piloted the soft drinks experiment with 270 Amazon Mechanical Turk (MTurk) participants making hypothetical choices. As shown in the top left panel of Figure A.8 below, we estimate that on average, consumers underweight the health costs of sugary drinks by about $\$2$ per 12-pack of 12-oz drinks. The labels have an average treatment effect (ATE) of decreasing WTP for the sugary drinks by about $\$0.50$. In an aggregate sense, these effects look like they are "in

the right direction," partially counteracting consumer bias. Unfortunately, as the top right panel shows, while the treatment effects of these labels are heterogeneous (the variance is significant and positive), they are not targeted to the consumers making the biggest mistakes (the covariance is approximately zero).

When these statistics are combined with our theoretical formula (assuming a pass-through parameter of $\rho = 1$ for simplicity), the bottom panel shows that in the absence of any taxes and subsidies, the labels do increase welfare by about \$0.50 per pack, as on aggregate they reduce over-consumption of the drinks. However, the bottom panel also shows that at the optimal sugary drinks tax, these labels in fact decrease social welfare. This is because the average decrease in consumption generated by the labels is no longer beneficial, and thus their highly heterogeneous but poorly targeted effects simply create "noise" in consumer choices. Our preliminary finding of differential benefits of the labels in the presence and absence of a sugary drinks tax illustrates how the combination of our theoretical formula and measurement techniques can be used to quantify the nuanced economic effects of these instruments.

Figure A.8: Results from hypothetical choice pilot

Note: Estimates are calculated from a hypothetical choice pilot of 270 participants on MTurk.

We plan to keep using hypothetical choice pilots to test new labels, and plan to have a set of five labels in the incentivized choice experiment.

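### The printed formula for Cov[τ, γ] omits the control arm, so any no-label change in willingness to pay that is related to bias is counted as label targeting

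*SAP*

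**What the plan says.** The SAP's Econometric details model WTP as "w_{ijk}(T) = v_{ijk} + \gamma_{ik} + \tau_{ik}(T) \cdot I(j = 2"), with true value v indexed by decision set (1 = no label for anyone, 2 = label or control). Bias γ carries no decision-set index. Four identifying assumptions follow:

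1. The mean of v is stable: "E[v_{ijk}|T] \text{ does not depend on } T \text{ or on } j".
2. The change v2 − v1 is uncorrelated with τ.
3. The error γ − γ̂ is uncorrelated with τ.
4. The error γ − γ̂ is uncorrelated with the change in v: "Cov}[\gamma_{ip} - \widehat{\gamma}_{ik}, v_{ijk} - v_{ij'k}] = 0" (the subscript p is read here as k).

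Two estimators are then said to follow. The variance of label effects averages "Var[\Delta w_{ij} | T = t] - Var[\Delta w_{ij} | T = 0"] over product pairs, so the control arm is subtracted. The covariance with bias averages "j (Cov[\Delta w_{ij}, \hat{\gamma}_i | T = t"], with no control term. Under Estimating bias, the proxy γ̂ is reported "with a standard deviation of 1.26". Sample Size and Power says the covariance interval will "have width of approximately 0.26 dollars squared". Related Preliminary Work says of the pilot labels that "they are not targeted to the consumers making the biggest mistakes (the covariance is approximately zero").

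**The concern.** Cov[τ, γ] is the study's targeting measure. It enters ½Var[τ] + Cov[τ, γ], the welfare effect of a label under an optimal tax, and is doubled in Var[τ] + 2Cov[τ, γ]. Subtracting control in the variance formula concedes that WTP varies between the two decision sets even without a label. If some of that variation is related to bias, the label-only covariance credits it to the label. Examples would be participants with high or low bias revising their answers differently on a second pass. Because the pilot covariance was near zero, a modest drift could create apparent targeting, or apparent mistargeting. The randomised comparison that would remove it is available but is not used for this quantity.

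**Working it through.** **The plan's own figure.** √(1000/180) = 2.357 and 0.50/2.357 = 0.212, which agrees with the stated factor of 2.4 and treatment-effect width of $0.21. The covariance width of 0.26 cannot be rebuilt directly, because the pilot covariance width is not given.

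**Algebra.** γ cancels from the within-person difference, so in a labelled arm Δw = (v2 − v1) + τ and

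Cov[Δw, γ̂ | T = t] = Cov[τ, γ̂] + Cov[v2 − v1, γ̂].

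- Assumption 3 turns the first term into Cov[τ, γ].
- Assumption 4 turns the second term into Cov[v2 − v1, γ]. It does not remove it.
- Assumption 1 restricts means only and is not conditional on γ.
- Assumption 2 concerns τ, not γ.

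The theoretical framework lets bias covary arbitrarily with true values, so it does not help. In the control arm τ = 0, hence Cov[Δw, γ̂ | T = 0] = Cov[v2 − v1, γ̂], which is exactly the leftover term. The difference between arms is Cov[τ, γ̂], which equals Cov[τ, γ] by assumption 3.

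**Check by simulation.** Two million subjects per arm, all four assumptions satisfied, SD(γ) = 1.26, true Cov[τ, γ] = 0:

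| Assumed slope of v2 − v1 on γ | Cov[v2 − v1, γ] | Printed formula | Control subtracted |
|---|---|---|---|
| −0.2 | −0.318 | −0.316 | 0.001 |
| −0.1 | −0.159 | −0.159 | 0.000 |
| 0 | 0 | 0.000 | 0.000 |
| 0.1 | 0.159 | 0.159 | 0.000 |
| 0.2 | 0.318 | 0.316 | −0.002 |

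**Size against the planned precision.** A zero-mean drift of slope b on γ̂ adds b × 1.26² = 1.5876b. For b = 0.02, 0.05 and 0.10 this is 0.03, 0.08 and 0.16 dollars squared (0.06, 0.16 and 0.32 in Var[τ] + 2Cov). The planned half-width is 0.26/2 = 0.13, reached at b = 0.13/1.5876 = 0.082.

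**How often the label-only interval misleads.** The pilot width of $0.50 on 90 v 90 implies Var(Δw|0) + Var(Δw|t) = 90 × (0.50/3.92)² = 1.464. With Var(Δw|t) = Var(Δw|0) + Var[τ], Var(Δw|t) = (1.464 + Var[τ])/2. With 500 per arm and covariance near zero, the label-only SE is 1.26 × √(Var(Δw|t)/500). The chance that the 95% interval excludes a true zero is about Φ(δ − 1.96) + Φ(−δ − 1.96), where δ = 1.5876b/SE. For Var[τ] = 0.5: Var(Δw|t) = 0.982, SE = 0.0558, and at b = 0.05 δ = 0.0794/0.0558 = 1.42, giving 30%.

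| Assumed Var[τ] | b = 0.02 | b = 0.05 | b = 0.10 |
|---|---|---|---|
| 0.25 | 9% | 33% | 86% |
| 0.5 | 9% | 30% | 81% |
| 1.0 | 8% | 25% | 72% |

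The limiting case Var[τ] = 0 gives 10%, 38% and 91%, but the pilot reports a positive variance. Simulation with 500 per arm agrees to within about two percentage points. In the same runs the control-subtracted estimate averaged 0.00 with coverage of about 95%.

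**Width after the fix.** 3.92 × 1.26 × √(1.464/500) = 0.267 whatever Var[τ] is. Label-only widths are 0.204, 0.219 and 0.245 for Var[τ] = 0.25, 0.5 and 1.0, so the interval widens by factors of 1.31, 1.22 and 1.09.

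**Sign of the optimal-tax welfare term.** Starting from Cov = 0, drift reverses the sign of ½Var[τ] + Cov only if b is below −½Var[τ]/1.5876. This is −0.079, −0.157 or −0.315 for Var[τ] = 0.25, 0.5 or 1.0. Positive drift cannot reverse it.

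**The case against.** The strongest reply is that a term was dropped in typing. The power section's widths fit a two-arm difference: 0.21 × 1.26 = 0.265 against the stated 0.26, and for older adults 0.36 × 1.26 = 0.454 against 0.45, taking the stated 0.36 as given. A label-only covariance would be narrower. This assumes similar Δw variances in the arms and covariance near zero, and the SAP does not say it. The section also has other slips: the index j changes from decision set to product, and assumption 4 has a stray subscript. That assumption does no other work in the two formulas, so it may have been meant to remove this very term. All of this is plausible, but it supports a correction. Either the formula lacks its control term and the stated precision describes a different estimator, or an identifying assumption is missing.

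The second reply is that the drift may be negligible. γ̂ comes from Part I, two to three days before both decision sets, so it shares no same-session response error with Δw. Under assumption 1 the drift averages zero, so it would have to change sign across the range of γ̂. Nothing in the documents supports one value of b over another. This stands as a limit on the consequence. It does not supply the missing assumption, since real change in v related to γ would survive the waiting period.

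A third point also stands. The calibration treats the pilot's per-item interval as if it came from one Δw per participant, whereas the SAP's Var[τ] averages product-level variances. The exclusion rates and widening factors are therefore indicative.

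**Conclusion.** The concern holds. As printed, the targeting estimator equals Cov[τ, γ] + Cov[v2 − v1, γ] and does not follow from the four assumptions. That conclusion is algebraic and rests only on the SAP's model. The practical size is unknown: every slope above is assumed, and with no bias-related drift the formula is unbiased. A slope of about 0.08 dollars per dollar of bias would shift the estimate by the planned half-width. The estimated sign of the covariance is therefore exposed, given a pilot value near zero. The sign of welfare at the optimal tax is less exposed, since it needs negative drift beyond thresholds that depend on Var[τ], which the text does not give. The average treatment effect is not affected. This should be corrected before the analysis.

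**What to change.** Replace the summand with Cov[Δw, γ̂ | T = t] − Cov[Δw, γ̂ | T = 0], keep the averaging over product pairs, and base inference on the participant. Carry the result into Var[τ + γ] − Var[γ] and the welfare expressions. Randomisation then cancels the drift term, assumption 3 is still required, and assumption 4 is no longer needed. A treatment-by-γ̂ regression coefficient multiplied by Var(γ̂) gives the same quantity only if Var(γ̂) is equal across arms, which randomisation ensures in expectation.

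If the label-only formula is kept, state Cov[v2 − v1, γ] = 0 as an explicit assumption, and report the control-arm covariance of Δw and γ̂ with its confidence interval as a check.

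The cost is one line of SAP text, with no new participants or data. The interval is wider than a label-only one, but at about 0.27 dollars squared the stated 0.26 essentially stands.

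### The listed identifying assumptions leave the level of the bias proxy free, so the no-tax welfare statistic needs a further unlisted condition, E[γ − γ̂] = 0

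*SAP*

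**What the plan says.** In the SAP, Statistical Design, Econometric details, willingness to pay is w = v + γ in the first decision set and w = v + γ + τ in the second (v true value, γ bias, τ label effect). The conditions are introduced so: "We make the following identifying assumptions, which essentially state that the measurement error in" γ̂ is independent of the label effects. Four conditions follow:

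1. The mean of v does not vary with arm or decision set.
2. Cov[v₂ − v₁, τ] = 0.
3. Cov[γ − γ̂, τ] = 0.
4. Cov[γ − γ̂, change in v] = 0.

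Formulas for Var[τ] and Cov[τ,γ] come next, and then "From this, it we can also immediately obtain the following statistics":

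- Var[τ+γ] − Var[γ] = Var[τ] + 2Cov[τ,γ]
- E[(τ+γ)²] − E[γ²] = Var[τ] + 2Cov[τ,γ] + E[τ]² + 2E[τ]E[γ]

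The discussion of Proposition 1 gives the role of the two added terms: "In the absence of a financial instrument, the welfare effects of the label also depend on" them.

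The level of γ̂ is set under Estimating bias, by a formula with coefficients, price and elasticity from a cited study and two zero-bias benchmarks. The nutrition benchmark is an expert score of 0.92, "and 1 represents perfect self-control". The resulting mean is 1.95 with a standard deviation of 1.26. No sensitivity analysis of that level is described.

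**The concern.** Covariances are unchanged when a constant is added to a variable. Conditions 3 and 4 are the only ones that involve γ̂, and both hold equally well if γ̂ is too high or too low by the same amount for everyone. The first statistic contains no mean of γ. The second does. Presenting both as consequences of one list gives them the same standing, although the second rests on a stronger condition.

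What is at stake is one half of the contrast reported under Related Preliminary Work, where labels raise welfare with no tax and lower it at the optimal tax. The optimal-tax half does not depend on the level of bias. With the covariance near zero, the no-tax gain depends on it entirely, because Var[τ] + E[τ]² cannot be negative and the only term that can make the statistic negative is 2E[τ]E[γ].

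**Working it through.** **Inputs.** From Related Preliminary Work: E[τ] about −0.50, Cov[τ,γ] about 0, ρ = 1, and a no-tax gain of about $0.50 per pack. From Estimating bias: E[γ̂] = 1.95. Not in the text: Var[τ] (described only as significant and positive), D_p and the mark-up μ.

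**Step 1, the plan's own figure.** The $0.50 gain cannot be strictly reproduced without those three values. Write S for the second statistic. With ρ = 1 and μ = 0, Proposition 1 reduces to ΔW = ½ · S · D_p, so a gain means S < 0. If also D_p = −1 (assumption), a gain of 0.50 means S = −1.00.

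**Step 2, identification.** Replace γ by γ + c and v by v − c. Keep τ and γ̂.
- w is unchanged in both decision sets, since the constants cancel.
- Condition 1: the mean of v shifts by −c in every arm and decision set, so it still does not vary.
- Condition 2: v₂ − v₁ and τ are unchanged.
- Conditions 3 and 4: γ − γ̂ gains a constant, so the covariances are unchanged.
- Var[τ] + 2Cov[τ,γ] is unchanged.
- S changes by 2E[τ]c.

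The same data and the same four conditions are thus compatible with different values of S. E[τ] is identified from the mean change in w under condition 1, so E[γ] is the only missing moment, and E[γ − γ̂] = 0 supplies it.

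**Step 3, simulation check** (n = 400,000; E[τ] = −0.5, Var[τ] = 0.70, Cov = 0). For every c below, the mean w stayed at 2.949 and 2.451, the three covariances in conditions 2 to 4 stayed within 0.001 of zero, and the estimate that uses E[γ̂] stayed at −0.995.

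| c | −1.5 | −1.0 | −0.5 | 0 | +1.0 |
|---|---|---|---|---|---|
| true S | 0.500 | 0.001 | −0.498 | −0.998 | −1.996 |

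**Step 4, size.** S = Var[τ] + 2(0) + (−0.50)² + 2(−0.50)E[γ] = Var[τ] + 0.25 − E[γ]. At E[γ] = 1.95 this is Var[τ] − 1.70. A level error c changes S by −c. The sign changes at E[γ] = Var[τ] + 0.25. Over assumed values of Var[τ]:

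| Var[τ] | S at 1.95 | break-even E[γ] | error c needed |
|---|---|---|---|
| 0.25 | −1.45 | 0.50 | −1.45 |
| 0.50 | −1.20 | 0.75 | −1.20 |
| 0.70 | −1.00 | 0.95 | −1.00 |
| 1.00 | −0.70 | 1.25 | −0.70 |
| 1.50 | −0.20 | 1.75 | −0.20 |

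Var[τ] = 0.70 is the value that matches Step 1. With ρ = 1 and no mark-up, a reported gain requires Var[τ] below 1.70.

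**Step 5, the general break-even.** Setting ΔW in Proposition 1 to zero gives E[γ] = −[(Var[τ] + 2Cov[τ,γ])/ρ + E[τ]² − 2μE[τ|p]] / (2E[τ]). With ρ = 1 and μ = 0 this is −(Var[τ] + 2Cov[τ,γ] + E[τ]²)/(2E[τ]).

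**The case against.** The level is not hidden. Econometric details says that it takes the bias estimates as given, and Estimating bias then states the bias model, the benchmarks and the resulting mean. The second displayed line is also an algebraic identity. On this view the extra condition is implicit and only a label is missing.

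Part of this stands: the SAP does supply a number for E[γ̂], and the identity is correct. But a number for the proxy's mean is not an assumption that the proxy is right on average, and the SAP's own gloss claims only independence of the error from τ. Independence does not imply mean zero. Saying that bias arises from knowledge and self-control does not fix the zero point either; the benchmarks do.

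A reader might go further and infer that a modest change of benchmark reverses the no-tax result. The documents do not support that. If p is in cents per ounce (assumption; the unit is not stated), the scale is 3.63 × 1.44/1.39 = 3.76. Moving the self-control benchmark from 1 to 2/3 then lowers E[γ̂] by 3.76 × 0.825/3 = $1.03, to $0.92. At Var[τ] = 0.70 that takes S from −1.00 to about +0.03; at 0.50 it leaves S at about −0.17. The outcome turns on an unreported variance, and the 2/3 benchmark gives people who report no over-drinking a negative self-control term, which nothing in the SAP supports. It serves as a stress test only.

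**Conclusion.** The second statistic, and so the no-tax welfare result, does not follow from the four listed conditions alone. It also needs E[γ − γ̂] = 0, and randomising the labels gives no information about that. This is exact algebra and would remain if every borrowed coefficient were known without error. On the pilot's figures, with ρ = 1 and no mark-up, each dollar of level error in γ̂ moves the statistic by one dollar squared, from a starting point of Var[τ] − 1.70.

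Two stronger readings should be avoided. The first is that the pilot's no-tax gain is wrong or its sign unstable; without Var[τ] that cannot be said. The second is that the listed conditions fully secure the targeting and optimal-tax result. That result is immune to level error, but the SAP's covariance formula has a gap of its own: Cov[Δw, γ̂] = Cov[τ, γ̂] + Cov[Δv, γ̂], where Δ is the change between decision sets. Condition 4 makes the last term equal to Cov[Δv, γ], not to zero.

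**What to change.** 1. List E[γ − γ̂] = 0 as a separate assumption, needed only for the no-tax statistic. Do not state alongside it that the listed conditions fully support the covariance formula. That formula also needs Cov[Δv, γ̂] = 0, or subtraction of the control-arm covariance.
2. For each label, plot the no-tax statistic over a range of E[γ], marking E[γ̂] and the break-even mean bias (short form for ρ = 1 and no mark-up, general form otherwise). Give intervals from a bootstrap that resamples participants. Where E[τ] is near zero the ratio is unstable, so show the curve and omit the ratio. Note that the comparison of E[γ̂] with break-even reverses direction if E[τ] > 0.
3. State the no-tax conclusion as conditional on the level of bias. An alternative self-control benchmark may be shown as an illustration, but not as a rule for claiming or denying a gain.

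The cost is a few lines of SAP text and one extra curve per label, with no new data. The downside is slightly more analysis and a no-tax conclusion stated conditionally.
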